## **11.5 Monitoring Procedures**

Details will be outlined in the Study Monitoring Plan. Key risk indicators may include, but are not limited to, adverse event reporting, compliance to the protocol, enrollment, and the Investigator Site File. In the event where a particular site is not performing as expected, appropriate intervention may be made. Interventions may include, but are not limited to, retraining, site audits, enrollment suspension or site termination.

Safety monitoring on a real-time basis will be implemented, such that the sponsor, and independently the Principal Investigator, will be able to take appropriate steps to manage emergent safety signals, e.g., to put on hold or stop the clinical trial in case a safety signal is observed. In addition, an external Data Safety Monitoring Board will perform a review of the safety data after the roll-in procedures and if a safety event is triggered.

## **11.6 Maintenance of Records**

Documents that must be provided to the Sponsor prior to any study Site Initiation include:

- Medical Device Agreement
- Financial Disclosure and Arrangements of Clinical Investigator
- Investigator's Signed Protocol Signature Sheet
- Study Site Personnel CVs and Medical Licenses
- A copy of the IRB-approved informed consent form (ICF) and other adjunctive material (e.g., marketing flyers) to be used in the study, including written documentation of IRB approval for these materials
- Name and address of the IRB and a statement/document that attests that it is organized and operates according to GCPs and applicable laws and regulations (i.e., the FWA number and/or IORG number and/or a list of the IRB's current members)

## **11.7 Record Retention**

During or after the study, the appropriate regulatory agency may inspect study records at the investigational site. Since inspection may arise at any time, records should be kept current at all times. The Sponsor must be advised of any request by a regulatory agency to visit or inspect the laboratory.

Records must be maintained for:

- A period of at least 2 years after the last approval of a marketing application in an ICH region when there are no pending or contemplated marketing applications in an ICH region.
- A period of at least 2 years after the formal discontinuation of development of the investigational product(s).

These documents should be retained for a longer period of time if required by the applicable regulatory requirement(s) or if required by the Sponsor.

## 11.8 Publications

The protocol, procedures, and data pertaining to this study will be treated as confidential information. Publication of data and/or information derived from these studies must be done with the prior review and approval of the Sponsor. Scientific personnel may share authorship with investigators on abstracts, oral presentations and manuscripts. The first author will be the person assuming primary responsibility for the abstract or manuscript.

# 12 STATISTICAL METHODS AND SAMPLE SIZE

## 12.1 General Overview

All of the data will be verified and archived by Fresenius Kabi, USA, Lake Zurich, IL. Any change to the data analysis methods described in this protocol will require an amendment ONLY if it changes a principal feature of the protocol. Any change to the data analysis methods described in the protocol, and the justification for making the change will be described in the final study report.

The primary objective of this study is to demonstrate that the per procedure rate of significant hypotensive adverse events (SHAEs) using the Aurora Xi New Nomogram algorithm is less than double the SHAE rate under the Aurora Xi Optimized Nomogram algorithm. This is a multi-center randomized controlled trial in which plasma donors at three centers will be recruited and randomized in a 1:1 ratio to use the Aurora Xi New Nomogram algorithm or the Aurora Xi Optimized Nomogram algorithm.

Standard summary statistics (e.g., count, mean, standard deviation, minimum, median, and maximum values) will be reported for subject and procedure parameters.

One secondary objective is to demonstrate that the per procedure rate of severe hypotensive adverse events (IQPP DAE Classification 1.5 or 1.6) under the Aurora Xi New Nomogram algorithm is non-inferior to the per procedure severe hypotensive adverse event rate using the Aurora Xi Optimized Nomogram algorithm. Analyses will be carried out as in the primary analysis with this binary donation-specific response, log-link, identity variance function, and working independence assumption. A robust variance estimate will be used for inference to provide protection against a within-donor association in responses of successive procedures within clusters defined by donor identifying numbers.

The Statistical Analysis Plan will expand on the data analysis to be conducted for the remaining endpoints.

## 12.2 Determination of Sample Size

The sample size requirement is calculated based on a model for correlated binary data in which the marginal mean is modelled with a log-link function and set by

$$\log \mu_{ij} = \beta_0 + \beta_1 X_i$$

where  $X_i = 1$  for an individual assigned to the experimental arm and  $X_i = 0$  otherwise. Note that center is not controlled for in the sample size calculation. Controlling for center is anticipated to improve power by explaining variation in the response, so this is a conservative approach to estimating the sample size since the power is anticipated to be at least the desired power. For the sample size derivation, the fitted model uses the identity variance function and a working independence assumption with a robust variance derived from a joint model to account for the association in the responses from serial donations from the same donor. The calculations require specification of the mean  $\mu_x = E(Y_{ij}|X_i = x)$  and the variance  $V_x = \text{var}(Y_{ij}|X_i = x)$  of the response  $Y_{ij}$  to procedure  $j$  from donor  $i$  as well as the within-donor correlation. If  $\kappa_x$  and  $\mu_x$  is the mean and variance for the number of procedures for a donor in arm  $x$  and  $n$  is the total number of donors to be recruited, then the asymptotic (large sample) variance (*asvar*) of the estimator of the log relative rate satisfies

$$\text{asvar} \left\{ \sqrt{n} \left( \hat{\beta}_1 - \beta_1 \right) \right\} \simeq \frac{2V_0}{\kappa_0 \mu_0^2} \left( 1 + \frac{\delta_0 \rho}{\kappa_0} \right) + \frac{2V_1}{\kappa_1 \mu_1^2} \left( 1 + \frac{\delta_1 \rho}{\kappa_1} \right)$$

where  $\delta_x = \nu_x + \kappa_x^2 - \kappa_x$  and  $\rho$  is the within-donor correlation in the responses over successive procedures from the same donor. The sample size involves computation of an asymptotic robust variance estimate for the estimator based on a multivariate binary probability mass function with specified marginal event rates of SHAE for the Test and Control arms and a specified exchangeable correlation for responses over successive procedures within the same donor, using the conditional linear family (Preisser and Qaqish, 2014) of multivariate binary models. In addition to the response model, a zero-truncated negative binomial model is used for the number of donation procedures over time from each donor which accommodates between-donor heterogeneity in the procedure rate. The number of required donors is computed based on the constraint

$$P \left( \hat{\beta}_1 + 1.96 \sqrt{\text{asvar}_A(\hat{\beta}_1)} < \beta_{1M} | \beta_1 = \beta_{1A} \right) = 0.80$$

which ensures that the probability that the upper limit of a two-sided 95% confidence interval for the relative risk is below  $RR_M = \exp(\beta_{1M}) = 2$  with 80% power if the true log relative rate is determined by  $\beta_{1A}$ . Based on historical data, the event rate in the control arm is expected to be 0.221% thus setting  $p_C = 0.00221$  or equivalently  $\log \mu_0 = \beta_0 = \log(0.00221)$ . The margin of non-inferiority is specified as  $\exp(\beta_{1M}) = 2$ . To accommodate a slight elevation in the SHAE rate under the alternative hypothesis of non-inferiority, the sample size calculations will be carried out with  $\exp(\beta_{1A}) = 1.2$ , corresponding to a 20% relative increase in the SHAE rate (still within the region of non-inferiority).

Accommodating a slight increase helps ensure that the power objectives are met to demonstrate non-inferiority even if there is a 20% relative increase in the SHAE rate using the Aurora Xi New Nomogram. In order to achieve 80% power when  $\exp(\beta_{1A})$  equals 1.2,

when donations are taken over an 8-week follow-up period, a sample size of  $n = 11,519$  donors may be required. The total number of procedures across all trial participants of  $n \times \kappa$  will target 51,720 for the primary endpoint evaluation.

### 12.3 Analysis Data Sets

The study endpoints include the primary and secondary objectives. The Intent-to-Treat Analysis (All Subjects Enrolled) will consist of individuals who signed an informed consent form, were randomized, and had at least one procedure initiated during the study. Outcomes for all procedures will be analyzed and responses attributed to the arm to which donors were randomized. The Per-Protocol Analysis will restrict attention to procedures in which the device used (Test or Control) matched the arm to which the donor was randomized.

The hypothesis for the primary endpoint for the Intent-to-Treat and Per Protocol analyses is shown as

$$H_0 : RR \geq RR_M \text{ (inferiority)} \quad \text{vs.} \quad H_A : RR < RR_M \text{ (non-inferiority)}$$

Summary statistics (mean, standard deviation, median, minimum, maximum and count) will be presented for continuous parameters with their 95% confidence limits as applicable. Discrete parameters will be presented by total number and percentage. Summary statistics will be presented for continuous parameters or descriptive statistics for discrete parameters.

### 12.4 Analyses

Standard summary statistics (e.g., number, mean, standard deviation, minimum, median, and maximum values) will be reported for subject and procedure parameters. Analyses will be performed to evaluate the primary objective to demonstrate that the per procedure rate of significant hypotensive adverse events (SHAEs) using the Aurora Xi New Nomogram algorithm is less than double the rate of SHAE rate under the Aurora Xi Optimized Nomogram algorithm in Section 12.2.

Additional analysis will be performed to demonstrate that the per procedure rate of severe hypotensive adverse events (IQPP DAE Classification 1.5 or 1.6) under the Aurora Xi New Nomogram algorithm is non-inferior to the per procedure severe hypotensive adverse event rate using the Aurora Xi Optimized Nomogram algorithm. Analyses will be carried out as in the primary analysis with this binary procedure-specific response, log-link, identity variance function, and working independence assumption. A robust variance estimate will be used for inference to provide protection against a within-donor association in responses of successive procedures with clusters defined by donor identifying numbers. The same non-inferiority margin will be used as for the primary response.

A detailed statistical procedure will be outlined in the Statistical Analysis Plan for the other secondary endpoints.

#### **12.4.1 Efficacy Analysis**

There are no Efficacy Analysis planned as the purpose of this study is to demonstrate safety. A variety of secondary analyses (described in Section 3.2) will be carried out to assess the effectiveness of the Test procedure for the collection of greater volume, etc.

#### **12.4.2 Additional Analyses**

Once the minimum number of procedures has been achieved for the primary endpoint analysis, a review of the data will occur. The primary endpoint will be evaluated based on the population/procedures up to this point. If this analysis demonstrates non-inferiority of the Test arm relative to the Control (i.e., the primary objective), then a specific analysis of subgroup sample sizes will be conducted. If any subgroup targets have not been achieved, the sites will be asked to specifically enroll and collect procedures from the target subgroup(s) only, until the subgroups in question meet their target minimum number of procedures. Each participant can donate for up to 8 weeks. The subgroup analysis will be conducted once a sufficient number of procedures for each subgroup is recorded. The primary endpoint will not be re-evaluated with the additional collections performed during this target enrollment and donation period to ensure that the primary analyses are based on a representative sample of donors and procedures.

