**Study Design:** This is a multicenter, prospective randomized controlled clinical trial to evaluate the Aurora Xi New Nomogram for the collection of plasma. The Test group will utilize the Aurora Xi Plasmapheresis system with New Nomogram (software version 2.0) and the Control group will utilize the Aurora Xi Plasmapheresis System with Optimized Nomogram (software version 1.3). Subjects will be retained in the assigned study arm (Test/Control) throughout their participation in the study period. Participants will donate for up to 8 weeks for the primary endpoint analysis, resulting in at least 51,720 plasmapheresis procedures. At that point, the primary endpoint analysis will take place. If noninferiority is demonstrated for the primary endpoint, but subgroup enrollment is not judged to be sufficient, an optional extension period will begin, during which collections and enrollment will continue from specific subpopulations (first-time donors, female donors, young donors, and low body weight donors). Collections performed during the optional extension period will not be included in the primary endpoint analysis but will be included for secondary endpoint analyses / subgroup analysis.

It is anticipated that enrollment will take approximately 6-9 months. Prior to enrollment, all subjects will be required to provide a signed informed consent for this research study and meet all standard requirements for the plasma collection center. Subjects will be considered enrolled at the time of venipuncture for the first on-study collection procedure. Plasmapheresis subject evaluations will be completed pre-procedure, during the procedure, and post-procedure between the date of the first on-study collection and up to 2 weeks after the last on-study collection.

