### Rule 1: Subject Death

If at any time during the study there are:

- One or more subject deaths reported.

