## 12.11 Stopping Rules

After the primary endpoint evaluation period, the extension period, if needed, will end at the discretion of the sponsor, when a sufficient sampling of each high-risk subgroup has been achieved. Due to potential difficulty recruiting participants from each high-risk subgroup, the sponsor reserves the option to stop the study prior to or at any time during this optional extension period.

- If the primary endpoint fails, then the extension phase will not occur.
- If enrollment during the extension period for any of the subgroups is not sufficient to complete the study in a reasonable time period (up to 3 months), then the extension period could be stopped at the discretion of the sponsor.

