The following is the list of secondary parameters and how they will be analyzed. If any subgroup target number of donations has not been achieved after the overall sample size has been met, sites will be asked to continue to collect donations over an extended period of follow-up specifically for donors in the target subgroups who are already on-study, and to focus recruitment of new individuals to those of each target subgroup(s) until the minimum number of procedures is met for each subgroup. Each subject in any target subgroup may donate only during their 8-week participation period. If enrollment during the extension period for any of the subgroups is not sufficient to complete the study in a reasonable time period (defined as an extension period of up to 3 months), then the extension period could be stopped at the discretion of the sponsor.

1. Incidence rate of SHAEs per donor status (first-time)

Analysis will be carried out to estimate the relative risk of significant hypotensive events for first-time donors. First-time donors are defined as individuals who have not donated plasma in the preceding six months. Individuals retain their first-time status only for their first procedure during the study period. Since there is no clustering of responses, a simple robust variance estimate will be used to provide protection against misspecification of the

identity variance function. Once the model is fitted, a point estimate and a 95% confidence interval will be computed for the relative rate of SHAE for first time donors. With a relative rate for a SHAE = 1.2 and the non-inferiority margin of $RR_M = 4$, a sample size of $n = 1,329$ procedures is required for this subgroup to have 80% power.

2. Incidence rate of SHAEs for female donors

The log linear model stated above will be fitted for female donors with the same specifications as the primary analysis with a binary procedure-specific response: a log-link, identity variance function, and working independence assumption for procedures from the same donor. Once the model is fitted, a point estimate and a 95% confidence interval based on a robust variance estimate will be computed for the relative rate of SHAE for female donors. With a relative rate for a SHAE = 1.2 and the non-inferiority margin of $RR_M = 2.5$, a sample size of $n = 26,366$ procedures is required for this subgroup to have 90% power.

3. Incidence rate of SHAEs for donors ≤ 20 years of age

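### The optional extension can open without any scheduled look at SHAEs by arm within the high-risk subgroup it will enrol, and the SAP does not repeat the protocol's start condition

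*Protocol*

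**What the plan says.** **Start condition in the protocol.** The summary states: "If noninferiority is demonstrated for the primary endpoint, but subgroup enrollment is not judged to be sufficient, an optional extension period will begin". Section 12.4.2 has the same two parts. Overall non-inferiority comes first, "then a specific analysis of subgroup sample sizes will be conducted", and if any target is unmet "the sites will be asked to specifically enroll and collect procedures from the target subgroup(s) only". Section 12.11 adds the bar: "If the primary endpoint fails, then the extension phase will not occur".

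**Start condition in the SAP.** Section 4.2 reads: "If any subgroup target number of donations has not been achieved after the overall sample size has been met, sites will be asked to continue". That sentence contains no non-inferiority condition. SAP section 6 refers to Protocol Section 12 for trial termination, so the bar reaches the SAP only indirectly.

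**When subgroup outcomes are examined.** Protocol 12.4.2: "The subgroup analysis will be conducted once a sufficient number of procedures for each subgroup is recorded".

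**Safety oversight.**
- Protocol 6.11 lists safety concerns as a ground for termination.
- Protocol 11.5 provides real-time safety monitoring, under which the sponsor or the Principal Investigator can hold or stop the trial.
- Protocol 12.6 lets the DSMB develop its own criteria and request unblinded data, and makes its decision binding on the sponsor.
- Protocol 12.10 lists two triggers: "One or more subject deaths reported" at any time, and six or more class 1.5 or 1.6 events during the first half of planned procedures.
- Protocol 12.5 hides the randomization category in the roll-in review.
- Protocol 12.11: "the sponsor reserves the option to stop the study prior to or at any time during this optional extension period". The reason given there is recruitment difficulty.

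**The concern.** The extension is confined to donors whom Protocol 5.1 itself calls high risk, and Protocol 9.3 accepts that larger collected volumes may raise the chance of adverse events. When the extension is decided, subgroup SHAEs by arm have already been recorded, yet the written gate asks only about the overall result and the subgroup's procedure count.

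For a small subgroup the overall relative rate is a weak screen, because most events come from other donors. A subgroup with a marked excess on the Test arm can therefore sit inside a trial that passes overall, be short of its target, and qualify for more enrolment under the rule as written. What is at stake is avoidable exposure of those donors.

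**Working it through.** **1. The plan's own figure.** Total procedures = 2[(1−p0)/p0 + (1−p1)/p1](1.96+0.8416)²/(ln 2 − ln 1.2)² × design effect.
- With p0 = 0.00221 and p1 = 1.2 × p0 = 0.002652, the bracket is 451.5 + 376.1 = 827.6.
- Without clustering, N = 2 × 827.6 × 7.849/0.2609 ≈ 49,784, and power at 51,720 is 81.5%.
- The stated 51,720 implies a design effect of 51,720/49,784 = 1.039. The documents give neither the within-donor correlation nor the variance of procedures per donor, so the exact total can be neither confirmed nor faulted. I carry 1.039 forward.

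**2. How small the subgroups are.** Against 51,720, the SAP targets are 1,329 (2.6%, first-time), 2,514 (4.9%, age 20 or less), 4,827 (9.3%, 124 lbs or less) and 26,366 (51%, female).

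**3. Implied control rate, 124 lbs or less.** The documents give no subgroup rate. Solving the same formula for n = 4,827 (margin 4, RR 1.2, 80% power, design effect 1.039) gives (1 + 1/1.2)/p − 2 = 429.0, so p = 0.425%. Without the design effect it is 0.41%.

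**4. One data set that the rule lets through.** The subgroup is at half its target, 1,207 procedures per arm.
- Subgroup: 5 Control and 20 Test SHAEs. RR 4.0; SE = √[1.039(1/20 + 1/5 − 2/1,207)] = 0.508; 95% CI 1.48 to 10.8.
- Whole trial, 25,860 per arm: 57 Control events (25,860 × 0.00221) and 57 + 15 = 72 Test events. RR 1.26; SE 0.180; 95% CI 0.89 to 1.80. This passes the margin of 2.
- The count, 2,414 of 4,827, is short, so about 2,413 more low-weight procedures would be sought.

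**5. How often.** Simulation of 400,000 trials per scenario: Poisson counts, control rate 0.425% in the subgroup, 0.221% overall, RR 1 in all other donors, Wald limits with design effect 1.039, and 0.5 added to the subgroup counts. Harm is called visible when the subgroup's own 95% CI lies above 1. The subgroup supplies 965 × 0.00425/57.15 = 7% to 1,448 × 0.00425/57.15 = 11% of control-arm SHAEs at 40% and 60% of target, and overall RR = 1 + share × (RR − 1). Excess SHAEs in the extension = (remaining procedures/2) × 0.00425 × (RR − 1), with 2,896 or 1,931 remaining.

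| Subgroup RR | Overall RR | Overall NI passes | Harm visible, given pass | Excess SHAEs in extension |
|---|---|---|---|---|
| 2 | 1.07-1.11 | 91-88% | 11-21% | 6-4 |
| 3 | 1.14-1.22 | 85-78% | 41-62% | 12-8 |
| 4 | 1.22-1.32 | 78-64% | 72-89% | 18-12 |

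Each range runs from 40% to 60% of target. At 25% of target and RR 4, harm is visible in about 41% of passing trials. At RR 1.5 and 40-60% of target it is about 3-7%. First-time donors and donors aged 20 or less behave almost identically.

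**6. Which listed DSMB triggers are still live.** Half of 51,720 is 25,860, passed well before the extension. Even if every subgroup target were collected afresh (1,329 + 26,366 + 2,514 + 4,827 = 35,036), half of 86,756 is 43,378, still below 51,720. Only the death trigger remains.

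**The case against.** **Someone could intervene.** A reader might infer that sites must enrol into a subgroup with visible harm and that nobody could prevent it. The documents do not support that. Protocol 6.11, 11.5 and 12.6 give the sponsor, the investigator and the DSMB power to act on safety, and nothing confines that power to the main phase. The extension is called optional, and Protocol 12.11 lets the sponsor stop before or during it. This part of the objection stands. What it leaves unanswered is that each safeguard depends on somebody choosing to look at a subgroup by arm, and no such look is scheduled. Protocol 12.4.2 does mention a review of the data, but the steps it then names are the primary endpoint and subgroup sample sizes.

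**The SAP does not stand alone.** A reader might also infer that the SAP opens the extension on counts alone. Its sentence reads that way, but SAP section 6 defers to Protocol Section 12, which bars the extension if the primary endpoint fails. This is an omission to reconcile, not a rival rule.

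**The scenarios are severe.** RR 4 is not a prediction; it is the SAP's own margin for these three subgroups. The accrual shares, control rate and RR of 1 elsewhere are assumptions, and at RR 2 or below visible harm is uncommon. The visibility criterion is mine, not the plan's. The dilution argument does not extend to female donors, whose target is about half of all primary procedures.

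**The DSMB charter was not available.** It may already contain such a look. If so, the protocol and SAP need only refer to it.

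**Conclusion.** The concern holds as a gap in the stated gate. The protocol opens the extension on overall non-inferiority plus a short subgroup count, with subgroup outcomes analysed only after the target is met. No by-arm subgroup review is scheduled first, the severe-event trigger has lapsed, and the roll-in review hides the arm. The start conditions in Protocol 12.4.2, Protocol 12.11 and SAP 4.2 must be reconciled.

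The size depends on the true subgroup effect: a minor matter near RR 2, and a substantial one at RR 3 to 4, where a passing trial would often already show the excess. These figures rest on a back-solved control rate, assumed accrual and no effect in other donors. They illustrate what the gate permits and do not forecast what will happen. The existing general safeguards make this a worthwhile, inexpensive improvement rather than a fatal defect.

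**What to change.** - **One start condition.** Use the same wording in Protocol 12.4.2, Protocol 12.11 and SAP 4.2: overall non-inferiority has been shown, as the protocol already requires, and the subgroup is short of its target.
- **A DSMB look first.** Before a subgroup's extension opens, the existing DSMB receives a closed table of main-phase SHAEs, and of class 1.5/1.6 events, by arm within that subgroup, and has no objection. The criterion is left to the DSMB charter.
- **Confidentiality.** The sponsor receives only the recommendation, not the subgroup results.

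The look can only withhold enrolment, so it gives no extra opportunity to claim non-inferiority. The cost is a few sentences in two documents and one closed table. The downside is that the extension may open some days later, or not at all for one subgroup, which would leave that subgroup's secondary analysis short of its planned size.
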